The recently opened Metabolic Unit, a state-of-the-art metabolic phenotype characterization laboratory, has the capability, through the temperature-controlled and fast response metabolic chambers, to analyze changes in the human physiology in controlled environmental conditions. This hypothesis-driven natural history protocol/physiology is thus aimed, by taking full advantage of the capabilities of the Metabolic Unit, to the detailed characterization of the physiological response to the stimulation of endogenous BA secretion and to characterize the role of BAs in the postprandial thermogenesis.

Study Hypotheses

1) If BAs have an endocrine/paracrine action on BAT-equivalent tissue in humans, the acute pharmacological stimulation of the endogenous BAs secretion by CCK and/or the oral administration of BAs will result in an increase in thermogenesis similar to the one

observed in the postprandial period of a high-fat meal, and greater than the one observed in a high-carbohydrate one.

2) If the raise in circulating BAs is coincidental but not causative of the increase in thermogenesis observed in the postprandial period, we do not expect to observe any change in EE after an oral dose of BAs. Consequently, if the increase in thermogenesis observed in the postprandial period is secondary to endocrine effects of CCK, but not to BAs *per se*, we will observe an increase in EE after CCK infusion but not after an oral dose of BAs.

3) Conversely, if the postprandial thermogenesis is secondary to calorie intake, irrespective of macronutrient composition, while no thermogenic effect will be observed after acute administration of BAs (or the pharmacological stimulation of the endogenous BAs secretion), a comparable increase in thermogenesis will be observed after a high carbohydrate or a high-fat meal.

4) If the postprandial thermogenesis is dependent to the secondary macronutrient composition, a differential increase in the thermogenesis will be observed after a high carbohydrate as compared to a high-fat meal.

Aim of the study:

1) To characterize the metabolic and hormonal responses to changes in endogenous BAs secretion following CCK stimulation or pharmacological administration of BAs.

2) To characterize the role of BAs and macronutrient composition in postprandial thermogenesis.

Secondary aims

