The primary endpoint of this mechanistic study is the analysis in changes in energy expenditure in response to changes (pharmacological or diet-induced) in serum bile acids concentration. The data will be analyzed using Analysis of Variance (ANOVA) and, should the data suggest an interaction, we will explore statistical models including delta in bile acid concentration, thyroid hormone concentration, and macronutrient diet (as a categorical data). Power analysis: Although this is a pilot study, we use previously published data comparing the effect on PPT (31) to help power the study, The PPT was 7.6-10.1% of the total energy intake, with a standard deviation of 2.6%. If we detect a desired difference of 2.0% in PPT with CCK or high fat diets, 28 study subjects will be needed to provide an 80% statistical power (α error of 0.05, using a two-tailed independent t-test design). We plan to enroll 30 volunteers considering the possibility of missing values.

Research use, storage, and disposition of human subject's samples and data

Serum, plasma, and nucleic acid samples will be coded and stored in a -80°C refrigerator located in the PI's laboratory. Tissue samples will be coded and stored in a liquid nitrogen tank located in the PI's laboratory. A registry of the samples location will be kept in the PI's office. This will allow the PI and the AIs to analyze research data in relation to clinical data stored in the Medical Record Department. Data and samples will be retained for the foreseeable future in order to allow secondary analyses after the completion of the protocol. Such analyses include association studies for known mutations of genes involved in the energy, carbohydrate, thyroid hormone and glucose metabolism, as well as gene scanning for novel mutations. Serum, plasma and nucleic acids samples will be similarly utilized for future association studies of known and novel markers of energy, carbohydrate, thyroid hormone and glucose metabolism. The PI will inform the IRB in case of loss of data/samples secondary to intrusion in the laboratory or database.

Possible Risks and Hazards:

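### Two hypotheses are supported by an absent or comparable energy response, but the analysis plan has no rule to tell no difference from an inconclusive result

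*Combined protocol and SAP*

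**What the plan says.** The Study Hypotheses section lists competing explanations and the observation that would mark each one. Several of these marks are the absence of a difference.

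- **Hypothesis 2, first part:** if bile acids are a bystander, "we do not expect to observe any change in EE after an oral dose of BAs".
- **Hypothesis 2, second part:** if CCK itself is the driver, "we will observe an increase in EE after CCK infusion but not after an oral dose of BAs".
- **Hypothesis 3:** if calorie intake alone matters, "no thermogenic effect will be observed after acute administration of BAs" (or after stimulation of endogenous secretion), and "a comparable increase in thermogenesis will be observed after a high carbohydrate or a high-fat meal".

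Hypothesis 4 is the direct rival of Hypothesis 3 on the meals: it predicts that the two responses differ.

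The Statistical analysis section is the only statistical text. Its primary endpoint reads "The primary endpoint of this mechanistic study is the analysis in changes in energy expenditure" in response to changes in serum bile acids. It plans an ANOVA and, if an interaction is suggested, exploratory models with bile acid change, thyroid hormone and diet. The sample size rests on this premise: "If we detect a desired difference of 2.0% in PPT with CCK or high fat diets". It uses an SD of 2.6%, 80% power and a two-tailed independent t-test at 0.05, which gives 28 subjects, with 30 enrolled. The study is described as a pilot.

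**The concern.** Choosing between Hypotheses 3 and 4, and reading the null half of Hypothesis 2, requires the analysis to tell three results apart: a difference, a difference too small to matter, and too little information to say. The plan provides only for the first. It does not define *comparable*, sets no bound on *no change*, and has no category for an inconclusive contrast. A non-significant comparison is the only output it offers that could be taken as support for a null prediction.

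At stake is the mechanistic conclusion. A real but moderate bile acid effect, or a moderate difference between meals, could be non-significant and then be taken to show that bile acids play no part or that macronutrient content is irrelevant.

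**Working it through.** **Inputs.** From Statistical analysis: target difference 2.0 points of energy intake, SD 2.6, two-sided 0.05, 28 subjects (30 enrolled). From Study design and methods: each volunteer receives every condition. The within-person correlation r is not given; I assume 0, 0.3 and 0.5, with 0.7 as a check.

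**The plan's own figure.** Normal approximation: n = 2 × (1.96 + 0.84)² × (2.6/2.0)² ≈ 26.5, so 27 per group. The exact independent t-test gives 27.5, so 28 per group with 80.7% power. The 28 reproduces as a per-group number. In the cross-over the same 28 people supply both conditions, which is close to a paired design at r = 0 (paired t: 29 at r = 0, 16 at r = 0.5).

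**Precision of a within-person contrast, n = 28.** SD of the difference = 2.6 × √(2(1 − r)); SE = SD/√28; half-width = t × SE, with t on 27 df of 2.052 (95%) or 1.703 (90%).

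| | r = 0 | r = 0.3 | r = 0.5 |
|---|---|---|---|
| SD of difference | 3.68 | 3.08 | 2.60 |
| SE | 0.695 | 0.581 | 0.491 |
| 95% half-width | 1.43 | 1.19 | 1.01 |
| 90% half-width | 1.18 | 0.99 | 0.84 |

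At the expected SE, a result is non-significant when the estimate is below about 1.43, 1.19 or 1.01. Its 90% interval stays inside ±2.0 when the estimate is below 2.0 minus the 90% half-width: about 0.82, 1.01 or 1.16. So estimates of about 0.82 to 1.43 (r = 0) or 1.01 to 1.19 (r = 0.3) are non-significant yet do not exclude the plan's own target. At r = 0.5 that zone has closed.

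**How often each rule gives a null reading.** I simulated the paired mean (normal) and its SE (scaled chi-square, 27 df). *Combined* means non-significant and 90% interval inside ±2.0.

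| True difference | Rule | r = 0 | r = 0.3 | r = 0.5 | r = 0.7 |
|---|---|---|---|---|---|
| 1.0 | Non-significant | 72% | 62% | 50% | 28% |
| 1.0 | Interval inside ±2.0 alone | 40% | 51% | 63% | 82% |
| 1.0 | Combined | 40% | 48% | 47% | 28% |
| 1.5 | Non-significant | 45% | 30% | 16% | 3% |
| 1.5 | Combined | 17% | 18% | 14% | 3% |
| 0 | Combined | 75% | 90% | 95% | 95% |

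The interval rule alone is worse than non-significance from r = 0.5 upward. At r = 0.5 it also labels 16% of trials both significant and comparable. The combined rule removes that conflict and, as a subset of the non-significant results, can never give a null reading more often than non-significance does.

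**A tighter margin.** With 30 volunteers, true equality and a margin of 1.0 point, the interval rule succeeds in about 2%, 11% or 32% of trials at r = 0, 0.3 or 0.5. Reaching 80% would need 118, 83 or 60 volunteers.

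**The case against.** A reader might infer that the protocol accepts Hypotheses 2 and 3 whenever a test is non-significant, so that an inconclusive contrast would be reported as no effect. The documents do not say so. The hypotheses run from mechanism to expected observation, and no acceptance rule is written. The two-tailed 0.05 test belongs to the power calculation; the planned analysis is an ANOVA. The hypotheses also discriminate by pattern: the second part of Hypothesis 2 needs a positive CCK response as well as a null after oral bile acids. This stands. The defect is a missing rule and the risk that follows.

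A reader might also infer that an equivalence test at ±2.0 settles the matter at the planned size. It does not. The plan calls 2.0 a difference to detect, never a negligible one, and the table shows that the interval rule alone can mislead more often than non-significance.

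Nor does the 2.0 figure carry over directly to the drug days. The power statement names CCK and high-fat diets, not ursodiol. The measure is a percentage of energy intake, and the text specifies no test meal on the sincalide, placebo or ursodiol days (the procedure figure is not available).

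Finally, this is a pilot with aims of characterization. That lowers the stakes, but a small study has more need to separate no difference from too little information.

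**Conclusion.** The concern holds as a gap in the plan. Nothing separates *no effect* from *inconclusive* for the null predictions of Hypotheses 2 and 3. At half the design difference (1.0 point), 28 volunteers would give a non-significant result in about 72%, 62% or 50% of trials at r = 0, 0.3 or 0.5.

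The combined rule lowers the null reading to about 40%, 48% or 47%. Most of the benefit comes at low correlation. At 0.5 it is about three percentage points, and at 0.7 it vanishes. The figures rest on the plan's SD of 2.6, the assumed correlations and the use of the 2.0-point target as margin. They apply to the meal contrast and extend to the drug contrasts only by assumption.

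Even a result that passes supports only the statement that a difference of 2.0 points or more is excluded; it does not show that there is no effect.

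**What to change.** Add to Statistical analysis:

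1. Report every within-person contrast with its confidence interval.
2. Call the high-fat and fat-free meals comparable only if the difference is not significant **and** its 90% interval lies inside ±2.0 points. Word the conclusion as excluding a difference of 2.0 points or more.
3. Call a non-significant result whose 90% interval reaches 2.0 points inconclusive.
4. Report a significant difference as a difference, wherever its interval lies.
5. For ursodiol versus placebo and sincalide versus placebo, apply the same two-part rule with a justified margin in energy-expenditure units. The value 2.0% × 600 kcal = 12 kcal is only an assumed starting point, because no test meal is specified on those days.

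The cost is a few sentences, with no added volunteers or procedures. Some null results become inconclusive: at true equality about 20%, 5% or 0.5% of trials at r = 0, 0.3 or 0.5. The sponsor should also accept in advance that a 1.0-point margin is out of reach with 30 volunteers over that range.

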Postprandial thermogenesis, or “thermic effect of food” are terms that describe the increase in utilization of energy by the human body following a meal. The mechanisms involved in this process are believed to differ according to the type of food consumed, whether fat, protein or carbohydrate.

The bile acids (BAs), unique substances secreted by the gall bladder into the gut after a meal, play an important role in the absorption of fat and the management of cholesterol stores in the body. Recent studies suggest that BAs may also serve as regulators of energy expenditure (consumption) in the cells of our body by increasing the production of T3, an active form of thyroid hormone. T3 in turn is believed to increase the efficiency with which our bodies burn calories thereby generating heat. Although this process has been shown to be effective in rodents who demonstrated weight loss after treatment, the role of BAs in humans is poorly understood. Thus we do not know whether endogenous (produced by the body) or exogenous (taken as medication) BAs play a significant role in the maintenance of body weight. We hypothesize that, similarly to rodents, humans will respond to BAs by increasing energy expenditure via the production of the active form of thyroid hormone.

This randomized, cross-over study will look at changes in thyroid hormones and energy consumption in response to stimuli of endogenous BA secretion including dietary content, and to the intake of pharmacological doses of bile acids.

Following a two-day period of equilibration diet, 30 healthy volunteers will be randomly assigned to receive either a high-fat or high-carbohydrate isocaloric meal followed by a 6-hour metabolic chamber stay; the next day they will be crossed-over to the alternate intervention. During the following three days, the study subjects will again be randomized to receive either an intravenous injection of sincalide (the C-terminal octapeptide fragment of cholecystokinin) 0.04 mcg/kg or placebo and P.O. placebo, or I.V. placebo and 15 mg/kg of BA (ursodiol) with similar metabolic chamber stays and cross-over design.

The following parameters will be recorded and compared to placebo:

- Energy expenditure
- Substrate utilization
- Spontaneous movements
- Skin and core temperature
- Serial changes in circulating thyroid hormones
- Serial changes in bile acid serum concentrations

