The data gathered from this study will provide greater insight into the physiological and molecular mechanism(s) regulating the relation between endogenous bile acid secretion and energy metabolism in response to meals, as well as the role of BAs *per se* on energy metabolism.

Introduction

The overall energy balance is maintained by multiple redundant mechanisms regulating both energy intake and expenditure (EE) (1, 2). While a considerable amount of experimental and clinical data on the mechanisms regulating food intake is currently available, comparatively little is known about the regulation of postprandial thermogenesis (PPT). Classical studies by Rubner (3) and Lusk (4) have revealed the unique role of protein in PPT and termed it “specific dynamic action”. However, the roles of fat and carbohydrate, the major sources of energy intake, on PPT are less clear. Recently, Blaak et al. (5) have reported that the level of increase in 3-hr postprandial EE on a high-fat (95%) meal was lower in obese versus individuals. On the other hand, it has been shown that the metabolism of ^{14}C labeled dietary oleic acid to $^{14}\text{CO}_2$ began after 6 hours and end around 15 hours. Thus, the cause for this acute rise in PPT (<6 hours) cannot be attributed directly to the oxidation *per se* of the dietary fat.

BAs are steroid acids found predominantly in the bile of mammals. In humans, the most important BAs are cholic acid, chenodeoxycholic acid, and their conjugates with taurine and glycine (glycocholate and taurocholate). These molecules are derived from cholesterol and synthesized endogenously by the liver. Storage of excess bile acid takes place within the gall bladder from where it is available for secretion upon stimulation by such factors as cholecystinin (CCK) and high-fat diet. CCK, a gut-peptide hormone, naturally secreted by the duodenum in response to fat and protein rich meals causes increased production of hepatic bile, stimulation of gallbladder contraction and the relaxation of the Sphincter of Oddi, resulting in the delivery of bile into the duodenum. CCK and high-fat meals induce, together with an increase in the secretion of bile in the duodenum, a rapid rise in the plasma concentration of BAs(6).

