BAs have long been known to play a central role in lipid, fat soluble vitamin absorption and cholesterol catabolism, however in recent years an important role for BAs as signaling molecules has emerged. BA binding to FXR nuclear receptor can reduce expression of 7-alpha hydroxylase a rate-limiting enzyme in the synthesis of BAs in hepatic cells. Interestingly, BAs also act through an alternate pathway by binding a cell surface receptor TGR5. TGR5 is a G protein coupled receptor (GPCR), which upon binding with its ligand, leads to an increase in intracellular cAMP production. Recent evidence indicates that the cAMP-driven Type-2 Deiodinase gene (D2) is the naturally occurring target of the TGR5 signal pathway, ultimately resulting in an increase in the intracellular concentration of T3(7, 8) the active form of thyroid hormone.

This phenomenon has been demonstrated in BAT of mice and human skeletal muscle cells, tissues that express both TGR5 and D2 (8). In rodents fed a high fat diet, cholic acid prevented the development of diet-induced obesity by increasing energy expenditure (EE) and oxygen consumption in BAT through increased D2-mediated T4 to T3 conversion (8-11) This effect was not observed in D2 knockout mice or those rodents fed a regular diet. These data can thus be interpreted as an endocrine action of the bile acids whose postprandial serum levels increase would lead to an increase in D2 transcription and activity ultimately generating an increase in thermogenesis, thus responding in a homeostatic fashion to the caloric load. It is postulated that elevated intracellular cAMP and T3 concentrations induce the expression of uncoupling proteins (UCPs)(12). The UCPs, by reducing the “efficiency” of mitochondrial oxidative

phosphorylation, generate heat and thereby increase EE. In rodents this is achieved by the activation of the UCP-1 in the brown adipose tissue (BAT). Indeed, the UCP-1 gene is a thyroid-hormone dependent gene, and mice devoid of D2 are unable to produce non-shivering thermogenesis in response to cold exposure.

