In humans, the pattern of expression of D2 is strikingly different from the rodent(13, 14). Specifically, while adult individuals have no “anatomically defined” BAT, D2 and UCP-3 have been demonstrated in skeletal muscle, raising the possibility that this tissue, which is approximately 40-80% of the individual’s weight, could represent a “physiological equivalent” of BAT(10, 15). UCP-3 induction in skeletal muscle, similar to UCP-1 in rodents, may mediate an increase in EE after BA treatment thereby promoting weight loss and insulin sensitivity. Indirect evidence suggests that the D2-mediated T4 to T3 conversion plays a major role in the production of the circulating T3(16). Interestingly, two common genetic variants of the human D2 gene, Thr92Ala and -258 A/G SNP, have been associated both in cross sectional and in *in vitro* studies with changes in the enzymatic activity (17-20).

At the present, the role of BAs in the regulation of metabolism and energy expenditure in human BAT or “BAT-physiological equivalent” is unclear. *In vitro* evidence from cultured human skeletal muscle cells suggests that BAs increase the metabolic rate in this tissue. If this is true, one could hypothesize that the manipulation of circulating bile acid levels, by pharmacologic or dietary means, could result in an overall increase in EE, ultimately facilitating weight loss. Data available in the gastroenterology literature clearly demonstrate that either a high-fat meal or a single injection of CCK is able to generate respectively a 1.5 to 3-fold and 2-fold rises in circulating BAs (6, 21, 22) without any significant residual effect to the following day(23). Interestingly, the chronic use of bile acid salts for the treatment of primary biliary cirrhosis resulted in a mild increase in body weight(24). This finding was attributed to an overall improvement of the general (nutritional?) conditions of the patients (Dr [name], Mayo Clinic, *personal communication*). No data is currently available relative to the synchronous evaluation of energy expenditure and endocrine metabolism during manipulation of endogenous secretion or circulating levels of BAs.

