This natural history research protocol is designed as a double blind-cross over study with both pharmacological and nutritional interventions. During a seven-day stay at the NIH, volunteers will undergo five 6-hour clinical and experimental observations in the metabolic chamber. The timing of the experiments have been based on the observations of Hoffman and colleagues who have shown that the peak of BA's occurs at ~2 hours postprandially in a physiological pharmacokinetic model in man (25) and of Foberg et al. who showed that CCK induced a rise in serum bile acids (3 α -HBA) peaked at ~30 minutes and returned to baseline within 120 min (6). The overall outline of the study is reported in Figure 1. Briefly, eligible volunteers will be invited for a seven-day stay at the Metabolic Unit. After a two-day isocaloric equilibration diet, study volunteers will be randomly assigned to receive either a very low or high-fat isocaloric standardized liquid meal during a 6-hour stay in the metabolic chamber. After an 18-hour resting period the volunteers will then be crossed-over to the second type of meal. After an 18-hour resting period the volunteers will again be randomly assigned to receive an IV injection of sincalide (*Kinevac*, a sterile lyophilized powder of the C-terminal octapeptide fragment of cholecystokinin) 0.04 mcg/kg or placebo during a 6-hour stay in the metabolic chamber. After an 18-hour post infusion resting period, the volunteers will be crossed-over to the alternate study arm; during these two interventions the volunteers will also receive a P.O. placebo. The next day, after an 18-hour post infusion resting period from the previous metabolic chamber stay, the volunteers will receive an IV infusion of placebo and 15 mg/kg of ursodiol (as 300 mg capsules rounded up to the nearest 300 mg), and will undergo the same recording. The volunteers will be blinded relative to the composition of the IV and PO compounds. This study design is necessary to avoid carry-over effects of the PO BAs.

[figure not shown]
Fig. 1 Study protocol, overview

Equilibration diet: 2 days; Metabolic chamber stay: 6-hours

During each 6-hour stay in the metabolic chamber we will record the following parameters and will perform these procedures (Fig. 2, **A**: High fat/High carbohydrate meal, **B**: Sinicalide/IV Placebo-P.O. Placebo, **C**: IV Placebo-ursodiol):

Fig. 2 6-hour Metabolic Chamber stays, procedures and blood drawing protocol

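### A rise in energy expenditure after sincalide but not after oral ursodiol cannot separate CCK from endogenous bile acids, yet Hypothesis 2 assigns it to CCK and Hypothesis 1 can also claim it

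*Combined protocol and SAP*

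**What the plan says.** Hypothesis 2 makes two predictions about the oral dose. If the postprandial rise in bile acids is coincidental, "we do not expect to observe any change in EE after an oral dose of BAs". If the thermogenesis is an endocrine effect of CCK and not of bile acids, "we will observe an increase in EE after CCK infusion but not after an oral dose of BAs". Both are worded for bile acids as a class.

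The agent actually given is narrower. The opening summary writes "15 mg/kg of BA (ursodiol" and treats the two terms as one. Under Study design and methods, on the last study day "the volunteers will receive an IV infusion of placebo and 15 mg/kg of ursodiol". The Hospital stay section repeats this. No other bile acid is given by mouth.

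On endogenous bile acids, the Introduction says that in humans "the most important BAs are cholic acid, chenodeoxycholic acid, and their conjugates with taurine and glycine". It also says that a single CCK injection raises circulating bile acids about 2-fold. On energy expenditure in vivo it names one acid: "In rodents fed a high fat diet, cholic acid prevented the development of diet-induced obesity by increasing energy expenditure (EE").

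Hypothesis 1 predicts that, if bile acids act on the target tissue, thermogenesis will rise after CCK *and/or* after oral bile acids.

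**The concern.** The two drug probes do not deliver the same molecules. Sincalide mobilises the volunteer's own bile; the oral stay supplies ursodiol. Sincalide cannot by itself separate a CCK effect from a bile acid effect, because it changes both. The oral stay is there to break that tie, and it does so only if ursodiol behaves like the endogenous acids. The protocol neither states nor supports that assumption, and it does not limit the conclusion to ursodiol.

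What is at stake is the reading of the drug stays. A well-run trial could find a clear rise after sincalide, a precise null after ursodiol, and then report that CCK and not bile acids drives thermogenesis. The data would not support that statement.

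**Working it through.** No arithmetic settles this. The power statement under Statistical analysis is framed around CCK and high-fat feeding, and the argument below is the same at any sample size. The check is to set the explanations against the results each one predicts.

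Inputs from the protocol:
- Sincalide raises both CCK activity and endogenous bile acids (Introduction).
- The endogenous acids are chiefly cholic and chenodeoxycholic acid (Introduction).
- The oral agent is ursodiol alone (Study design and methods; Hospital stay).
- The TGR5/D2 pathway and the human muscle-cell evidence are described for bile acids generally. Cholic acid is the only one named in the in vivo energy evidence (Introduction).
- Nothing says that ursodiol acts on TGR5 or D2, raises energy expenditure, or stands for the endogenous acids.

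Predicted change in energy expenditure against placebo:

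| Explanation | Sincalide stay | Ursodiol stay |
|---|---|---|
| Bile acids act, ursodiol included | rise | rise |
| Endogenous acids act, ursodiol does not or does so too weakly to show | rise | null |
| CCK itself acts, bile acids do not | rise | null |
| Neither acts | null | null |

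Rows two and three are identical. Hypothesis 2 lists only row three for that pattern.

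Next, compare the two hypotheses. Under the *or* reading of Hypothesis 1, a rise after sincalide alone satisfies the bile acid hypothesis. Under Hypothesis 2 the same rise, with a null oral stay, is the signature of CCK without bile acids. The protocol gives no rule for choosing between them.

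The meal stays do not break the tie. The Introduction says that CCK is released in response to fat- and protein-rich meals and that a high-fat meal also raises bile acids, so the high-fat stay moves both together, as sincalide does.

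**The case against.** The strongest reply is that the protocol states its mechanism for bile acids as a class. TGR5 binding, D2 induction and the muscle-cell data are not tied to one acid, and nothing in the documents says that ursodiol differs from the others. This stands, and it limits the point. A reader might infer that the mechanism rests on cholic acid, or that ursodiol is inactive or weaker. The documents support neither. They show an unstated assumption, not a false one.

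A reader might also cite the remark that "the chronic use of bile acid salts for the treatment of primary biliary cirrhosis resulted in a mild increase in body weight" as human evidence against ursodiol. It should not be used: the protocol attributes that gain to better general condition in those patients, and it says little about a 6-hour stay in healthy volunteers.

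A third tempting reading is that any null ursodiol result is uninformative. That goes too far. If both stays are null, the sincalide stay itself speaks against endogenous bile acids, because it raised them without effect.

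It is also fair to say that Hypothesis 2 is a forward prediction and not a formal decision rule. The primary endpoint refers to changes in serum bile acids more broadly, and the analysis section foresees models that include the change in bile acid concentration. Those models are conditional on the data suggesting an interaction and name no particular acid. A correlation within the sincalide stay could not separate CCK from bile acids anyway, because one injection drives both. Separating the explanations is the evident purpose of Hypothesis 2, so its wording still matters.

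**Conclusion.** The point holds in a limited form. Of the four sincalide/ursodiol patterns, one (sincalide positive, ursodiol null) does not identify CCK as the cause, although Hypothesis 2 says it would, and the *and/or* in Hypothesis 1 lets it count for bile acids as well. Separately, a null ursodiol stay supports a conclusion about a single oral dose of ursodiol over the 6-hour stay, and not about bile acids as a class.

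This rests on the protocol's own statements that sincalide raises endogenous bile acids and that these are chiefly cholic and chenodeoxycholic acid, and on the absence of any statement that ursodiol represents them. It does not assume that ursodiol is inactive. The design, the data collected and the primary endpoint are unaffected. For a pilot mechanistic study this is a cheap improvement to the wording, not a fault in the design.

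**What to change.** Reword Hypotheses 1 and 2 so that:

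- (a) the ursodiol stay supports a conclusion only about a single oral dose of ursodiol over the 6-hour stay;
- (b) a rise after sincalide with no rise after ursodiol is declared in advance not to discriminate between CCK and endogenous bile acids;
- (c) the *and/or* in Hypothesis 1 is resolved, so that this pattern is not also claimed as support for a bile acid action.

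Optionally, add one descriptive analysis: the within-volunteer sincalide-minus-placebo change in energy expenditure set against the corresponding changes in cholic and chenodeoxycholic acid. Both acids are already listed under Laboratory testing. Label it associational, and state that it does not separate CCK from bile acids.

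The cost is a few sentences and a narrower claim from the ursodiol stay. Treatment, procedures, assays and sample size stay as they are.
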